Preeclampsia is a pregnancy-specific multisystem disorder of unknown etiology. PE typically affects 2%–5% of pregnant women and is one of the leading causes of maternal and perinatal morbidity and mortality, especially when the condition is of early onset (FIGO 2019). The exact nature of the primary event causing preeclampsia is not known. (Arias 2015). There is now good evidence that intake of low dose aspirin during pregnancy reduces the risk of pre-eclampsia. Uncertainty remains, about whether some women (in terms of risks) benefit more than others, what dose of aspirin is best & when in pregnancy treatment should ideally start. Therefore this study is developed to find out the role of aspirin in preeclampsia, the knowledge of which is expected to be used for prevention of preeclampsia.

Objective of the study:

Aim of study is to find out the effect of low dose aspirin in prevention of preeclampsia among pregnant women who are at high risk for developing preeclampsia.

Methodology

This Randomized clinical trial will be conducted in BIRDEM-II. Approval from Institutional Review Board will be taken. The study population will be pregnant women with risk factors for developing PE attending department of Obstetrics and Gynecology, BIRDEM-II. Pregnancy will be confirmed via USG. Then evaluation of risk factors of PE will be done by history taking, examinations & provided investigations. Those who will be eligible according to inclusion & exclusion criteria will be enrolled in the study. Trial information will be provided verbally & with a written information sheet. Participants will be randomized by lottery in a closed envelope, which will determine who receive aspirin daily & who will not. A total of 200 women will be included in the study, of whom 100 pregnant women having risk factors of developing pre-eclampsia will be in intervention group & another 100 pregnant women having risk factors for developing PE will be in control group. Intervention group will be prescribed to take 75 mg Aspirin daily after lunch starting from 12-19 weeks of pregnancy. Control group will not be prescribed to take Aspirin. For each and every subject separate data collection sheet will be prepared. Data will be collected from the patients using the structured design by history, clinical examination, urine & haematological investigations, ultrasonography of the patients. Both group of patients will get the usual advices & medications of pregnancy. All patients will be followed up at 19-24 weeks, 32-34 weeks of gestation, 36 weeks of gestation and weekly up to delivery. During follow up SBP & DBP will be carefully measured. Urine analysis will be done. Aspirin will be stopped either 36 weeks of pregnancy or when delivery occurs or when PE is diagnosed. Primary & Secondary outcome will be observed in both experimental & control group separately. Then analysis will be done by comparison of outcome of this two groups. Data will be analyzed using SPSS software.

RESULT: Result will be incorporated after completion of study.

CONCLUSION: Will be incorporated after completion of study.

Introduction

Preeclampsia is a multi-organ diseases of unknown etiology characterized by de novo development of hypertension and proteinuria after 20 weeks of gestation, sometimes progressing into a multi-organ cluster of varying clinical features.(Arias,2015). PE typically affects 2%–5% of pregnant women and is one of the leading causes of maternal and perinatal morbidity and mortality, especially when the condition is of early onset. Globally, 76,000 women and 500000 babies die each year from this disorder.(Poon L et al.2019). WHO estimates incidence of pre-eclampsia, to be seven times higher in developing countries (2.4% of live birth) than in developed countries (0.4%) (WHO, 2005). In Bangladesh, the incidence of preeclampsia is alarmingly high, about 20% of maternal death associated with PE and eclampsia (Landscape analysis,2015).

The risk of preeclampsia is increased three-fold in nulliparous women (Duckitt et al.2005).Among parous women the risk of PE in subsequent pregnancies depends on a prior history of PE (Harnandez-Diaz et al.2009).Other risk factors have been identified-maternal age ≥ 35 years,both short (< 12 months) & long interpregnancy intervals(> 6 years), ART, Family history of PE, obesity(BMI ≥ 30 kg/m[±]),comorbidities-hyperglycaemia in pregnancy, chronic HTN, renal disease, autoimmune disease-SLE,APS (FIGO,2019). In low socio economic status of women doubled the risk of pre -eclampsia and eclampsia (Ceron-Mireles et al. 2001).

Complication related to preeclampsia include preterm birth, intrauterine fetal growth restriction, placental abruption, maternal pulmonary edema, and eclampsia .The estimated incidence of eclampsia is 1-3 per 1000 preeclamptic patients. (CURRENT 2013).

In preeclamptic patients, prostacyclin synthesis is decreased & thromboxane production is increased, leading to vasoconstriction & platelet aggregation. Prostacyclin & thromboxane are products of the metabolism of Arachidonic acid by

the enzyme cyclooxygenase (Arias,2015).Aspirin (acetylsalicylic acid) is a nonsteroidal anti-inflammatory drug (NSAID) that works primarily through its inhibition of two cyclooxygenase isoenzymes (COX-1 and COX-2), which are necessary for prostaglandin biosynthesis. The effect of aspirin on COX-dependent prostaglandin synthesis is dose dependent. At lower dosages (60–150 mg/day) aspirin irreversibly acetylates COX-1, resulting in decreased platelet synthesis of TXA₂ without affecting vascular wall production of prostacyclin (Clarke et al.1991 & Patrono C, 1994). At higher doses, aspirin inhibits both COX-1 and COX-2, effectively blocking all prostaglandin production.

Research is focusing on prevention rather than treatment.Cochrane meta analysis published in 2004 reported that the administration of antiplatelet agents in high risk women could reduce the rate of PE by 19%(Lowe et al. 2014). World Health Organization (WHO) and NICE and the US Preventive Services Task Force (USPSTF) currently recommend daily low-dose aspirin therapy beginning at 12 weeks of gestation in patients who are considered to be at “high risk for preeclampsia” according to medical and obstetrical criteria. FIGO also recommends that 150mg aspirin at night should be commenced at 11-14⁺⁶ weeks of gestation and continued until either 36 weeks of gestation or when delivery occurs, or when preeclampsia is diagnosed (FIGO,2019).It has an excellent maternal/fetal safety profile in pregnancy.Therefore we decided to conduct a RCT in BIRDEM-II General Hospital to evaluate the role of low dose Aspirin in prophylactic treatment for prevention of PE.

1.2 Rationale of the Study

Preeclampsia is a hypertensive disorder specific to pregnancy that remains a significant cause of maternal & neonatal morbidity & mortality. Because of the potential negative health consequences of PE for women & newborns & the lack of effective screening mechanisms, preventing PE is an important component of prenatal care. Bangladesh Maternal Mortality survey(BMMS) 2010 revealed that eclampsia is the second most common direct cause of maternal death in Bangladesh followed by PPH.Among 5000 to 6000 maternal deaths each year,1000 to 1,200 are due to Eclampsia.(Landscape report,2015). Preeclampsia should be detected and appropriately managed before the onset of convulsions (eclampsia) and other life-threatening complications.

Since there is no curative treatment other than delivery, an intervention that could prevent preeclampsia would have a significant impact on maternal and infant health worldwide. Researchers have documented that low dose aspirin during antenatal check- up can prevent the development of PE who are at high risk of developing PE and also reduce the incidence of pre-term birth & fetal growth restriction. The relevant evidence of Asian women is very limited. Its safety is sometimes questionable. BIRDEM is a center of excellence where majority patients are diabetic and so many high risk for developing PE. Therefore, this study has been designed to evaluate the role of aspirin in reducing the incidence of preeclampsia including its dose and duration of use & safety of the drug.

1.3 Hypothesis

Research question:

Can low dose aspirin prevent preeclampsia in the pregnant women who are at risk of developing pre-eclampsia?

Hypothesis:

Low dose aspirin can lower the development of preeclampsia in pregnant women who are at high risk of developing preeclampsia

1.4 Objectives

General objective

- To find out the effect of low dose aspirin in prevention of preeclampsia among pregnant women who are at high risk for developing preeclampsia.

Specific objectives

- To find out the socio-demographic characteristics (Age, Occupation,
- To find out the primary outcome (occurrence of Preeclampsia) among both intervention & control group.
- To detect the secondary outcome among both groups: Maternal- Gestational HTN, Oligohydramnios, Preterm labor, Placental abruption, APH, PPH ; Fetal- LBW, Preterm birth , Small for gestational age, IUD,Still Birth, NICU admission among both groups.
- To compare the outcome of two groups.
- To analyze the possible association between Aspirin & Pre-eclampsia.

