outcome of placental abruption (6 trials in women with increased preeclampsia risk and 5 trials in women with low/average risk). Pooled analyses showed no statistically significant increase in abruption associated with aspirin (RR, 1.17 [95% CI, 0.93 to 1.48]; I² =36.4%).Eighteen trials reported on the outcome of perinatal mortality (with 4 smaller studies reporting no events).Pooled analyses (n = 22 848) on perinatal mortality (RR,0.92 [95% CI, 0.76 to 1.11]; 14 studies; I² = 0%) suggested no harm from low-dose aspirin. Nine trials (6 in women at increased preeclampsia risk and 3 in women at low risk; 22 760 women in total) reported on the outcome of postpartum hemorrhage. There was no evidence of a treatment effect (RR, 1.02 [95% CI, 0.96 to 1.09]) No evidence demonstrated that low-dose aspirin affected blood loss. The pooled relative risk for intracranial hemorrhage in neonates (6 studies; n = 22 158) was 0.84 (95% CI, 0.61 to 1.16), with low heterogeneity (I² = 27.1%; P = 0.23). Maternal death was a rare outcome and could not be evaluated.(Michael L. et al 2014).

Askie LM1 et al (2007) performed randomised trials of pre-eclampsia primary prevention. For women assigned to receive antiplatelet agents rather than control, the relative risk of developing pre-eclampsia was 0.90 (95% CI 0.84-0.97), of delivering before 34 weeks was 0.90 (0.83-0.98), and of having a pregnancy with a serious adverse outcome was 0.90 (0.85-0.96). Antiplatelet agents had no significant effect on the risk of death of the fetus or baby, having a small for gestational age infant, or bleeding events for either the women or their babies. (Askie LM1 et al (2007).

2. Materials and Methods

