2.9 Main outcome variables

Dependent variable

Pre-eclampsia

Independent variables

- Age
- Parity
- BMI
- Educational status
- Monthly income
- Occupation
- Blood pressure
- Proteinuria
- Aspirin

2.10 Operational definitions:

Hypertension: According to ACOG hypertension is defined as: BP equal to or greater than 140/90 mm of Hg, rise of systolic BP 30 mm of Hg or rise of diastolic BP 15 mm of Hg or more. (Arias“ 2015)

Chronic HTN: Hypertension that was present before pregnancy or it was diagnosed before 20th week of gestation.

Internationally agreed definition of PE is that of the International Society for the Study of Hypertension in Pregnancy (ISSHP) which is endorsed by FIGO.

Gestational hypertension: is defined as systolic blood pressure (sBP) at ≥ 140 mm Hg and/or diastolic blood pressure (dbp) at ≥ 90 mm Hg on at least two occasions measured 4 hours apart developing after 20 weeks of gestation in previously normotensive women.

Preeclampsia: is defined as gestational hypertension accompanied by ≥ 1 of the following new-onset conditions at or after 20 weeks of gestation:

1. Proteinuria (i.e. ≥ 30 mg/mol protein:creatinine ratio; ≥ 300 mg/l in 24 hour; or $\geq 2+$ dipstick)

2. Other maternal organ dysfunction:

Acute kidney injury (creatinine ≥ 90 $\mu\text{mol/L}$; 1 mg/dL)

Liver involvement (elevated alanine aminotransferase or aspartate aminotransferase >40 IU/L) with or without right upper quadrant or epigastric pain)

Neurological complications (including eclampsia, altered mental status, blindness, stroke, or more commonly hyperreflexia when accompanied by clonus, severe headaches, and persistent visual scotomata)

Hematological complications (thrombocytopenia—platelet count $<150\ 000/\mu\text{L}$, disseminated intravascular coagulation, hemolysis) or

3. Uteroplacental dysfunction (fetal growth restriction, abnormal umbilical artery Doppler waveform or stillbirth).

Superimposed PE on chronic hypertension:

- Women with chronic essential hypertension develop any of the above maternal organ dysfunctions consistent with PE
- Increase in blood pressure per se is not sufficient to diagnose superimposed PE
- In the absence of pre-existing proteinuria, new-onset proteinuria in the setting of a rise in blood pressure is sufficient to diagnose superimposed PE.

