--------------------	--------	---------------	---------------	---------

3)Education :Illiterate/Primary/SSC/HSC/Graduate/Postgraduate

Obstetric history

Married for

Para

Gravida

ALC

Number of foetus in present pregnancy Singleton / Multiple fetuses

Method of conception- Spontaneous/ OID/ ART

Previous history of Gestational HTN/ PE/ Eclampsia

Previous history of IUGR/ IUD/Still birth

Menstrual History

Cycle Regular/irregular

LMP

EDD

Family history : HTN/PE/Gestational HTN

Medical history: GDM /DM/Chronic

HTN/Hypothyroidism/APS/SLE

Drug history:

Hypersensitivity to Aspirin : Present /Absent

Levothyroxine sodium

Insulin

Others

Antenatal care Regular/Irregular

Clinical examination related informations

PHYSICAL EXAMINATION:

Date					
Height					
Weight					
BMI					
Anaemia					
Jaundice					
Edema					

Date					
Pulse (bpm)					
SBP (mmhg)					
DBP(mmhg)					
Proteinuria					

Proteinuria : trace, 1=+, 2=++, 3=+++ / Nil

Morning urine sample

Per abdominal examination:

Date					
Maturity					
SFH (cm)					
FM					
FHR					

During Follow up:

Complications :

Maternal- No complication/GIT upset / Gestational HTN /APH /oligohydramnios /

Preterm labour/others

Fetal- No complication /SGA/IUGR/IUD/PTB/others

Investigations :

Blood group & Rh typing

CBC

Urine R/M/E

Blood Sugar profile

HBsAg

VDRL

TSH

USG of pregnancy profile:

Mode of delivery: NVD/Caesarean section at weeks of gestation.

Outcome

Maternal: normal

PE - occurred /Not occurred

Gestational HTN

Oligohydramnios

PTL

APH

PPH

Fetal- Sex- weight- kg (Normal/SGA/LGA)

APGAR Score

PTB

NICU admission

IUD/ still birth

Others-

Date :

Signature of the investigator:

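### Placental abruption is a named secondary outcome separate from APH, but the data collection sheet has no item for it, so its capture rests on unprompted free text

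*Protocol*

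**What the plan says.** The relevant text is in the protocol.

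- **Section 1.4, Objectives.** The primary outcome is given as "To find out the primary outcome (occurrence of Preeclampsia) among both intervention & control group". The maternal secondary outcomes are "Maternal- Gestational HTN, Oligohydramnios, Preterm labor, Placental abruption, APH, PPH". Abruption and APH are two entries.
- **Section 1.2, Rationale.** The study is meant to evaluate the safety of aspirin as well as its effect on pre-eclampsia.
- **Section 1.5, Review of Literatures.** On abruption: "Pooled analyses showed no statistically significant increase in abruption associated with aspirin (RR, 1.17", with a 95% interval of 0.93 to 1.48.
- **Section 2.10, Operational definitions.** Pre-eclampsia "is defined as gestational hypertension accompanied by ≥ 1 of the following new-onset conditions at or after 20 weeks of gestation". Gestational hypertension is a blood-pressure criterion met "on at least two occasions measured 4 hours apart developing after 20 weeks of gestation in previously normotensive women". Superimposed pre-eclampsia in chronic hypertension has its own definition. Neither APH nor abruption is defined.
- **Data collection sheet, appendices.** The follow-up list begins "Maternal- No complication/GIT upset / Gestational HTN /APH /oligohydramnios" and ends with preterm labour and an open entry for other complications. The maternal part of the outcome section has pre-eclampsia (occurred or not), gestational hypertension, oligohydramnios, preterm labour, APH and PPH. An open line for other events comes after the fetal items.

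**The concern.** An outcome that the protocol promises to compare should have a place on the form that collects it. Abruption has none. Someone completing the sheet as printed would tick APH for a revealed abruption, and it would then be indistinguishable from any other antepartum bleed. A concealed abruption might not be entered at all. Because the trial has no placebo (section 2.16), whoever fills in the sheet may know the arm, and unprompted entries could then differ between arms for reasons unrelated to the outcome. An analysis rule written later cannot reliably recover what the form did not ask.

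A smaller matter concerns gestational hypertension. Pre-eclampsia that arises on new hypertension also satisfies the printed definition of gestational hypertension, yet the two are listed as separate outcomes and the protocol does not say whether a woman with pre-eclampsia counts in both rows. If she does not, and aspirin stops some women at gestational hypertension who would otherwise have progressed, that row rises with aspirin, and a hurried reader could take a benefit for a harm.

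**Working it through.** The protocol gives no figure for either point, so there is none to reproduce. The abruption point is a comparison of two lists.

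**Step 1. Outcome list against form.**

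| Maternal secondary outcome (1.4) | Follow-up list | Outcome section |
|---|---|---|
| Gestational hypertension | yes | yes |
| Oligohydramnios | yes | yes |
| Preterm labour | yes | yes |
| Placental abruption | **no** | **no** |
| APH | yes | yes |
| PPH | no | yes |

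Five of the six have a printed item in the outcome section. PPH is absent only from the antenatal follow-up list, where it would not be expected. Abruption is absent from both.

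**Step 2. What the form can still yield.** Abruption can be written in the open entries. A written entry is usable. A blank is not, because it may mean that abruption was absent or that nobody considered it. With APH undefined, an APH tick does not settle the matter either way.

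**Step 3. Can the gestational hypertension counts be recovered?** The sheet records pre-eclampsia as occurred or not, gestational hypertension as a separate item, and chronic hypertension in the medical history. Whether staff tick gestational hypertension only when pre-eclampsia is absent, tick both, or mix the two habits:

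- gestational hypertension without pre-eclampsia = gestational hypertension ticked and pre-eclampsia not occurred;
- any new hypertension = either item positive, in women with no history of chronic hypertension.

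Both counts are obtainable.

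**Step 4. Why the label is still worth adding.** Inputs: pre-eclampsia 8.71% in controls and 1.6% on aspirin (section 2.7), so averted d = 0.0871 − 0.016 = 0.0711. Assumptions, not in the document: gestational hypertension without pre-eclampsia in controls g = 5% to 15%; a share s of averted cases remains as gestational hypertension; no pre-eclampsia is superimposed.

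- RR without pre-eclampsia = (g + s·d)/g
- RR with or without pre-eclampsia = (g + s·d + 0.016)/(g + 0.0871)

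Example, g = 10%, s = 0.5: (0.10 + 0.03555)/0.10 = 1.36, and (0.10 + 0.03555 + 0.016)/0.1871 = 0.81.

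| g | RR without PE, s = 0 / 0.5 / 1 | RR with or without PE, s = 0 / 0.5 / 1 |
|---|---|---|
| 5% | 1.00 / 1.71 / 2.42 | 0.48 / 0.74 / 1.00 |
| 10% | 1.00 / 1.36 / 1.71 | 0.62 / 0.81 / 1.00 |
| 15% | 1.00 / 1.24 / 1.47 | 0.70 / 0.85 / 1.00 |

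In the intermediate case the two readings point in opposite directions. With 100 women per arm the example is about 10 against 14: RR 1.4, standard error of log RR = √(1/10 − 1/100 + 1/14 − 1/100) = 0.389, 95% interval exp(0.336 ± 1.96 × 0.389), about 0.65 to 3.0. That is not a difference the trial could distinguish from chance.

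**Step 5. Women with chronic hypertension.** They are eligible (section 2.8) but cannot meet a definition that requires onset "developing after 20 weeks of gestation in previously normotensive women". If they make up a share c of each randomised arm, the risks become (1 − c)·r₁ and (1 − c)·r₀, and the ratio is still r₁/r₀. Absolute risks are diluted; in expectation the relative risk is not biased.

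**The case against.** The best defence on abruption is that the form has open entries, and that section 2.11 says the questionnaire will cover every variable of interest. That defeats any claim that abruption cannot be counted or compared, which a reader might infer from the missing item. It does not make capture dependable: the attached sheet is the instrument at hand, it prompts for APH and not for abruption, and the open line in the outcome section comes after the fetal items.

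A reader might also infer that abruption is the one bleeding harm for which the cited literature points to excess. The protocol does not support that. The abruption RR of 1.17 is the largest of the pooled harm estimates in section 1.5, but its interval (0.93 to 1.48) includes 1. The PPH estimate is also slightly above 1 (1.02, interval 0.96 to 1.09), and the individual-patient meta-analysis described there found no significant effect on bleeding events. The case for the item rests on abruption being a named outcome in a study that also aims to assess safety.

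On gestational hypertension the objection largely succeeds. Listing it apart from pre-eclampsia is not an error, and "Women with chronic essential hypertension develop any of the above maternal organ dysfunctions consistent with PE" shows that the overlap is incomplete. Which of two recoverable counts to tabulate is a detail commonly left to an analysis plan, and replacing the outcome with a composite would be a matter of preference.

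**Conclusion.** The abruption point stands: a named secondary outcome has no item on the form, and following the form as printed captures it only through unprompted free text. The size cannot be stated, because the document gives no expected abruption rate and no basis for estimating how many events would go unwritten. The conclusion assumes that the attached sheet is the one that will be used.

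The gestational hypertension point is a labelling clarification only. A reader might infer that the comparison is invalid, that it double-counts women irretrievably, or that enrolling women with chronic hypertension biases it. The sheet's separate items and the randomised allocation argue against all three. An apparent rise appears only to the extent that averted pre-eclampsia remains as gestational hypertension, and the illustrative ratios rest on assumed background rates.

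The primary comparison, occurrence of pre-eclampsia, is not affected by either point.

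**What to change.** Before data collection:

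1. Add a yes/no item for placental abruption to the maternal part of the outcome section of the sheet, completed independently of APH.
2. State in section 1.4 or 2.10 whether the APH count includes abruption.
3. As a clarification, label the gestational hypertension row as without pre-eclampsia, and report any new hypertension (gestational hypertension or pre-eclampsia) beside it, from items already on the sheet.

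The cost is one item on the form and two or three sentences of protocol text, with no additional visits, tests or burden for the women. The first change is the one that depends on timing, since absent abruption entries may not be recoverable afterwards.

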3.5 Sampling technique

Simple randomization through lottery in a closed envelope. Randomization number will determine who will receive aspirin & who will not receive aspirin.

2.6 Study Procedure :

This Randomized clinical trial will be conducted in BIRDEM-II. Approval from Institutional Review Board will be taken. The study population will be pregnant women with risk factors for developing PE attending department of Obstetrics and Gynecology, BIRDEM-II. Pregnancy will be confirmed via USG. Then evaluation of risk factors of PE will be done by history taking, examinations & provided investigations. Those who will be eligible according to inclusion & exclusion criteria will be enrolled in the study. Trial information will be provided verbally & with a written information sheet. Participants will be randomized by lottery in a closed envelope, which will determine who receive aspirin daily & who will not. A total of 200 women will be included in the study, of whom 100 pregnant women having risk factors of developing pre-eclampsia will be in experimental group & another 100 pregnant women having risk factors for developing PE will be in control group. Experimental group will be prescribed to take 75 mg Aspirin daily after lunch from 12-19 weeks of pregnancy. Control group will not be prescribed to take Aspirin. For each and every subject separate data collection sheet will be prepared. Data will be collected from the patients using the structured design by history, clinical examination, urine & haematological investigations, USG of the patients. Both group of patients will get the usual advices & medications of pregnancy. All patients will be followed up at 19-24 weeks, 32-34 weeks of gestation, 36 weeks of gestation and weekly up to delivery. During follow up SBP & DBP will be carefully measured. Urine analysis will be done. Aspirin will be stopped either 36 weeks of pregnancy or when delivery occurs or when PE is diagnosed. Primary & Secondary outcome will be observed in both experimental & control group separately. Then analysis will be done by comparison of outcome of this two groups. Data will be analyzed using SPSS software.

2.7 Sample size determination:

Sample size is calculated using the following formula

$$n = \left[\frac{Z_{\alpha} \sqrt{p_1(1-p_1)} + Z_{\beta} \sqrt{p_2(1-p_2)}}{p_2 - p_1} \right]^2$$

Here, n= sample size

$p_1 = 1.6\%$ [Incidence of preeclampsia in experimental group (Rolnik et al., 2017)]

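### Placental abruption is a listed secondary outcome, separate from APH, but the data collection sheet has no field for it

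*Protocol*

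**What the plan says.** Protocol section 1.4 (Objectives) gives two lists of secondary outcomes, to be compared between the groups:

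- maternal: "Gestational HTN, Oligohydramnios, Preterm labor, Placental abruption, APH, PPH"
- fetal: "Fetal- LBW, Preterm birth , Small for gestational age, IUD,Still Birth, NICU admission among both groups"

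Abruption and APH are separate entries in the maternal list. Section 2.11 says that the structured questionnaire will cover every variable of interest.

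The data collection sheet (section 5, Appendices) records maternal events in two places. The follow-up complications line reads "No complication/GIT upset / Gestational HTN /APH /oligohydramnios" and goes on to preterm labour and a free-text option. The outcome block near the end has lines for preeclampsia, gestational hypertension, oligohydramnios, preterm labour, APH and PPH. Neither place mentions abruption. A last free-text line for other events closes the outcome block.

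Section 1.2 states that the study is meant to evaluate the role of aspirin "including its dose and duration of use & safety of the drug".

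**The concern.** An outcome that is to be compared between arms has to be asked for in the same way in every woman. Here the outcome list treats abruption as distinct from APH, while the form offers only APH. A tick for APH does not say whether the cause was abruption, and a woman with an abruption but no visible bleeding gives the person completing the form nothing to tick.

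A blank then has two meanings: no abruption, or abruption not asked about. The analysis stage cannot repair this, because no analysis plan can recover a variable that was not collected.

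The outcome also matters for a safety reading. Of the four pooled harm estimates in section 1.5, abruption has the highest relative risk (1.17, 95% CI 0.93 to 1.48). The upper limits for neonatal intracranial haemorrhage, perinatal mortality and PPH are 1.16, 1.11 and 1.09. None of the four shows a statistically significant harm, but abruption is the one for which a moderate increase is least clearly excluded.

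**Working it through.** The check compares the outcome list with the form. The plan gives no figure on this point to reproduce.

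**Step 1. Number of listed secondary outcomes (section 1.4).** Six maternal + six fetal = 12.

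**Step 2. Where each can be recorded on the data collection sheet.**

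| Listed outcome | Place on the sheet |
|---|---|
| Gestational hypertension | follow-up line and outcome block |
| Oligohydramnios | follow-up line and outcome block |
| Preterm labour | follow-up line and outcome block |
| **Placental abruption** | **none** |
| APH | follow-up line and outcome block |
| PPH | outcome block |
| Low birth weight | derivable from birth weight in kg |
| Preterm birth | follow-up line and outcome block |
| Small for gestational age | follow-up line and outcome block |
| Intrauterine death | follow-up line and outcome block (shared with stillbirth) |
| Stillbirth | outcome block (shared with intrauterine death) |
| NICU admission | outcome block |

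Recordable: 12 − 1 = 11. Without a field: 1 of 12, placental abruption.

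**Step 3. What the APH entry can say about abruption.** Let *a* be the number of women with APH in one arm, and suppose that nothing was written in free text. The number with an abruption and visible bleeding may then be anything from 0 to *a*. Those with an abruption but no visible bleeding come on top, in an unknown number. The APH count therefore fixes neither a rate of abruption in each arm nor a relative risk. The operational definitions in section 2.10 do not help, as they cover hypertension and preeclampsia only.

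**Step 4. Whether free text fills the gap.** The free-text entries can hold an abruption, but nothing prompts for it. Section 2.16 says that no placebo is used, and the sheet is headed with the study group, so whoever completes it can see the arm. Under these conditions unprompted recording may differ between arms, in either direction. The documents do not show that it will.

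**Step 5. Why counts should be reported descriptively.** With 100 women per arm, 0 events leaves a one-sided 95% upper limit of 1 − 0.05^(1/100) = 0.0295, about 3.0%. The two-sided 95% interval has an upper limit of 1 − 0.025^(1/100) = 0.0362, about 3.6%. These limits apply to any outcome at this sample size and do not measure the defect. They do presuppose that each zero is an answer to a question that was asked.

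**The case against.** The strongest reply is that very little is missing. Eleven of the 12 listed outcomes can be recorded, an abruption with bleeding would still be counted under APH, and free text remains for the rest. What is lost is a subclassification of APH plus the cases without visible bleeding. That is a fair measure of the gap, and it makes this a small form correction. It does not remove the point: the protocol itself lists abruption separately, and section 2.11 promises an instrument that covers all variables.

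A reader might infer more than the documents support:

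- *That the sheet cannot record bleeding or perinatal harm.* It has APH, PPH, intrauterine death and stillbirth, Apgar score and NICU admission.
- *That neonatal death and neonatal intracranial haemorrhage are outcomes left off the form.* Neither is listed in section 1.4. They enter only through the literature review, for example "The pooled relative risk for intracranial hemorrhage in neonates (6 studies; n = 22 158) was 0.84". A review of earlier studies does not define this trial's outcomes.
- *That outcome collection stops at delivery.* The phrase "36 weeks of gestation and weekly up to delivery" in section 2.6 describes the antenatal visits. PPH, birth weight, Apgar score and NICU admission can be completed only at or after birth, so the form itself reaches beyond that visit schedule.
- *That recording will differ between arms.* It may, as step 4 says, but nothing in the protocol establishes it.

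**Conclusion.** The point holds in a narrow form. One of 12 listed secondary outcomes, placental abruption, has no field on the data collection sheet and cannot be compared reliably between arms. The primary outcome and the other 11 secondary outcomes are not affected by this gap.

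The conclusion assumes that the sheet in the appendix is the form that will be used, and that an abruption would otherwise be entered under APH, entered as free text or not entered at all. How many abruptions would be misplaced or missed cannot be estimated, because the protocol gives no expected rate and no share without visible bleeding.

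Separately, the safety wording in section 1.2 is broader than what is collected on the baby after birth. This is a question of how far the stated purpose reaches, not an inconsistency between the outcome list and the form.

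**What to change.** Add one item to the data collection sheet, for both arms: placental abruption, yes or no, separate from APH, to be answered for every woman whether or not she bled. Report the counts by arm descriptively. The cost is one line on the form and the time to answer it, and no new test or visit is needed. If the form is already in use, the item would have to be completed from delivery records for women who have already delivered, as far as those records can be reached; the protocol does not say where they are held.

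Optional: either add an item for neonatal death before discharge, yes or no, so that perinatal deaths can be counted, or narrow the safety wording in section 1.2 to the events that the sheet collects. The first costs one more line and a check at discharge. The second costs a change to one sentence.
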